4. STUDY POPULATION

4.1. Population (base)

Pediatric patients undergoing in hospital minor invasive procedures.

4.2. Inclusion criteria

Patients are eligible if:

- 1 Age 1-16 years
- 2 Veinpuncture
- 3 Arterial line placement
- 4 Nasogastric tube placement
- 5 Urinary catheter placement
- 6 Removal of thoracic drain
- 7 Skin suture

4.3. Exclusion criteria

The following patients will be excluded if any of the following conditions is present

- 1 Age <1 year or > 16 years
- 2 Pneumothorax
- 3 Pneumoperitoneum
- 4 Pneumocephalus
- 5 Otitis media
- 6 Obstructive lung disease
- 7 Upper airway infection
- 8 Methylenetetrahydrofolate reductase (MTHF) deficiency
- 9 Vitamin B12 deficiency
- 10 Megaloblastic anemia

11 Folate deficiency (Vitamin B9 deficiency)

12 Bleomycin sulphate therapy

13 Neuropathy

14 Pregnancy

4.4. Sample size calculation

Based on previous published data estimated number of patients required to evaluate analgetic and anxiolytic effect as well as safety profile is between 32 and 90.^{8,9,10} We aim to observe 300 occasions that required oxygen: nitrogen 50%:50% gas mixture in order to draw unbiased conclusions.

5. METHODS

5.1. Study endpoints

5.1.1. Primary endpoint

Primary endpoint is evaluation of pain intensity using age specific pain scales.

5.1.2. Secondary endpoints:

Secondary endpoints are evaluation of cooperability of a child, anxiolysis, hemodynamic stability during inhalation and oxygenation as well as potential side effects.

Clinical outcome measures:

1 pain assessment as no/mild pain, assessed using age-based pain scales: FLACC up to 4 years, FACES 4-9 years and Numeric Pain Rating Scale 9-16 years;

2 anxiolytic effect defined as child's cooperability, that is executes orders or refuses to execute orders;

2 Level of sedation (desired level would be mild sedation defined as Ramsey score 2)

3 side effects: desaturation, bradycardia, hypotension

4 heart rate (HR), blood pressure (BP), hemoglobin oxygen saturation (SpO₂); monitored before, during and 30 minutes post gas mixture application

Desaturation is defined as SpO₂ < 95% on room air. Hypotension, hypertension, bradycardia, tachycardia are defined in accordance to age.

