Study protocol

Observation of clinical effects of oxygen: nitrogen 50%:50% gas mixture application for minor invasive procedures in pediatric patients

Correspondence

[name] PhD

Department of Anesthesiology

Institute for mother and child health care,

[name]

[name],

Serbia

Email: [contact]

Date

30.09.2024.

Summary

Rationale

Reducing pain and anxiety, avoiding psychological trauma associated with medical procedures are the focus of pediatric anesthesiologist in everyday practice. Nitrous oxide is a useful option for children who require procedural sedation. It is easy to apply, has satisfactory sedative and analgetic effects. Side effects are transient and vanish after discontinuation. It has been used for decades in pediatric emergency department as well for procedural sedation and analgesia.

Objective

The aim of this study is to evaluate the analgetic and anxiolytic profile of oxygen: nitrogen 50%:50% gas mixture for minor invasive procedures in pediatric patients.

Study design

Single center prospective observational cohort study.

Study population

Patients from 1 to 16 years of age admitted to department of anesthesiology and intensive care therapy, Institute for mother and child health care. Inclusion criteria: age 1-16 years; patients scheduled for following procedures : venepunction, arterial line placement, nasogastric tube placement, urinary catheter placement, removal of thoracic drain, skin suture. Exclusion criteria, presence one of the following conditions: age <1 year or > 16 years; pneumothorax; pneumoperitoneum; pneumocephalus; otitis media; obstructive lung disease; upper airway infection; methylenetetrahydrofolate reductase (MTHF) deficiency; vitamin B12 deficiency; megaloblastic anemia; folate deficiency (Vitamin B9 deficiency); bleomycin sulphate therapy; neuropathy, pregnancy.

Main study endpoints

Primary endpoint is evaluation of pain intensity following the implemented procedure.

Secondary endpoints are evaluation of anxiolytic effect, achieved level of sedation and observation of possible side effects such as hypotension, bradycardia and desaturation.

Nature and extent of the burden and risks associated with participation, benefit and group relatedness

The risks of prospective collection of demographic data, pain and anxiety scores during and after gas mixture application are negligible and the burden is minimal.

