2. OBJECTIVES & HYPOTHESES

2.1. Objectives

The aims of this study are:

- to evaluate the efficacy of oxygen: nitrogen 50%:50% gas mixture in achieving analgesia in pediatric patients requiring minor invasive procedures
- to evaluate the efficacy of oxygen: nitrogen 50%:50% gas mixture in achieving desired sedation in pediatric patients requiring minor invasive procedures
- to evaluate safety profile of oxygen : nitrogen 50%:50% gas mixture in achieving desired sedation in pediatric patients requiring minor invasive procedures

Minor invasive procedure investigated in this study are venepunction, arterial line placement, nasogastric tube placement, urinary catheter placement, removal of thoracic drain and kin suture

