6. PROTOCOL

Application of gas mixture will be conducted via suitable face mask, flow calculated to achieve ventilation minute volume (MV) in accordance to age, $MV \text{ (L/min)} = \text{tidal volume (Vt)} \times \text{respiratory rate (RR)}$.

6.1 Management of side effects:

- 1 desaturation – supplemental oxygen via face mask
- 2 hypotension – iv fluids, vasoactive drugs if needed
- 3 bradycardia – atropine 0,2 mg iv

Important note – side effects such as hypotension, bradycardia are not expected to occur regarding good pharmacodynamic profile of nitrous oxide on cardiovascular system. However, implementing and monitoring these possible effects during the study increases the safety profile of the study

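### Desaturation is defined only for room air, so a low SpO₂ reading during inhalation of the 50% oxygen mixture does not, as written, count as this side effect

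*Protocol*

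**What the plan says.** The outcome list in Protocol section 5.1.2 includes "side effects: desaturation, bradycardia, hypotension". A separate item in the list covers heart rate, blood pressure and SpO₂, which are "monitored before, during and 30 minutes post gas mixture application". The definition comes just after the list: "Desaturation is defined as SpO₂ < 95% on room air". The document contains no other definition of desaturation. The next sentence ties hypotension, hypertension, bradycardia and tachycardia to age and attaches no gas condition to them.

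The opening lines of 5.1.2 name as secondary endpoints "hemodynamic stability during inhalation and oxygenation as well as potential side effects". The Summary also lists "observation of possible side effects such as hypotension, bradycardia and desaturation". The third aim in section 2.1 is "to evaluate safety profile of oxygen : nitrogen 50%:50% gas mixture".

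On delivery, section 6 states: "Application of gas mixture will be conducted via suitable face mask". Section 6.1 uses the same word for a management step: "desaturation – supplemental oxygen via face mask".

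**The concern.** A side effect of an inhaled gas should be countable while the gas is being inhaled. Here the definition carries a condition, breathing room air, that is false for as long as the mask delivers the mixture. A child whose SpO₂ falls below 95% during inhalation and recovers before the mask comes off would not be a desaturation case under the text as written.

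Safety is one of three stated aims, and desaturation is one of only three side effects named in the outcome list. If the wording is followed, a report of few or no desaturations during inhalation would reflect the definition and not the children. If some staff follow the wording and others apply 95% on any gas, the count depends on who classified the reading.

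**Working it through.** The protocol gives no desaturation rate and plans no calculation on this point, so there is no figure to reproduce. The check sets the definition against the measurement schedule and the gas breathed.

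**Inputs**
- Threshold and condition: SpO₂ below 95%, on room air (5.1.2).
- Measurement times: before, during and 30 minutes after application (5.1.2).
- Gas during application: the 50%:50% mixture (2.1), by face mask (6). The protocol calls the other half nitrogen in some places and discusses nitrous oxide in others. That does not matter here, because a mixture with 50% oxygen is not room air in either case.
- Gas after a desaturation has been treated: supplemental oxygen (6.1).

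**Window by window, read literally**

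| Window | Gas breathed | Can a reading below 95% meet the definition? | Can it be a side effect of the mixture? |
|---|---|---|---|
| Before | Room air possible | Yes, if on room air | No, it precedes exposure |
| During | 50% oxygen mixture | No, the condition fails | Yes |
| 30 minutes after | Room air, or supplemental oxygen if given | Only if on room air | Yes |

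The one window in which the child is exposed to the mixture is therefore the one in which the definition can never be met.

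**Direction of the error.** Assume that each occasion is counted once if it has any qualifying reading (the protocol does not state the unit). Leave aside pre-gas readings and readings on supplemental oxygen. Let
- a = occasions with SpO₂ below 95% during inhalation,
- b = occasions with SpO₂ below 95% on room air afterwards,
- c = occasions with both.

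The literal count is b. The count with 95% applied on either gas is a + b − c. The shortfall is (a + b − c) − b = a − c, the number of occasions that were low during inhalation only. Since c cannot exceed a, the shortfall is zero or positive. The literal wording can lower the count or leave it unchanged, but cannot raise it. The protocol gives neither a nor c, so the shortfall cannot be put in numbers.

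**Supplemental oxygen.** The same condition also fails once supplemental oxygen is running. This is a minor extension: it mainly affects repeat events and their duration.

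**The case against.** The strongest reply is that the context shows what was meant. Desaturation is listed as a side effect of the gas, SpO₂ is monitored during inhalation, oxygenation is a secondary endpoint, and 6.1 manages desaturation as a side effect of application. Staff would probably count a low reading during inhalation whatever the wording says. This is a fair account of the likely intent and it limits the weight of the point. It does not repair the text, which states a condition that points the other way. Nor is this a detail left to an analysis plan, since the protocol itself fixes the definition.

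A second reply is that no data are lost, because SpO₂ is an outcome in its own right in every window. That stands. Low values can still be found where they were recorded; what is affected is whether they are classed as the named side effect.

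A third reply is that keeping 95% for readings on the mixture selects a threshold, although the same SpO₂ value does not mean the same on two gases, and that 6.1 ties the word to a treatment step. Both points have force. They are why the change should be limited to counting, why the gas should be recorded and the windows reported apart, and why the sponsor has to reconcile the two sections.

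A reader might go further and infer that the study is bound to report no desaturation at all, or none in its 300 planned occasions. The documents do not support that. Low readings on room air after the gas can still qualify, and the protocol plans no table by window and no confidence limit for this outcome.

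**Conclusion.** The point holds as a defect in a stated definition. Followed as written, the definition excludes every reading taken on the mixture from a named safety outcome, so the desaturation count can be too low in the exposure window. The size is unknown: it equals the number of occasions that are low during inhalation only, and it is zero if staff ignore the room-air condition.

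The conclusion rests on the literal reading of one sentence and on the mixture, not room air, being what the child breathes while the mask is on. It does not touch the primary pain endpoint, the other named side effects or the recorded SpO₂ values. It is not evidence that investigators have discarded, or would discard, low readings. It should be fixed because a safety aim depends on the label and the remedy is small.

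**What to change.** In section 5.1.2, for endpoint counting only:

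1. Remove the room-air condition, so that readings on the mixture are counted against the protocol's own figure of 95%. No new threshold is introduced.
2. Record the gas breathed at each low reading (mixture, room air or supplemental oxygen).
3. Report events during inhalation and events after it separately, because the same value does not mean the same on different gases.
4. List occasions with a pre-gas value already below 95% apart, since these cannot be effects of the mixture.

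Section 6.1 uses the same word for a management step. The sponsor must reconcile that use with the definition in 5.1.2; nothing here proposes when treatment should be given.

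The cost is one sentence and one data field. The event rate may look less favourable than under the present wording. Recruitment was set to run for 24 months from October 2024, and any occasions already observed can be reclassified only as far as the recorded SpO₂ values and the gas breathed allow. The protocol does not say whether SpO₂ is kept continuously or only at single points, so an early correction is worth more than a late one.

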6. PROTOCOL

Application of gas mixture will be conducted via suitable face mask, flow calculated to achieve ventilation minute volume (MV) in accordance to age, $MV \text{ (L/min)} = \text{tidal volume (Vt)} \times \text{respiratory rate (RR)}$.

6.1 Management of side effects:

- 1 desaturation – supplemental oxygen via face mask
- 2 hypotension – iv fluids, vasoactive drugs if needed
- 3 bradycardia – atropine 0,2 mg iv

Important note – side effects such as hypotension, bradycardia are not expected to occur regarding good pharmacodynamic profile of nitrous oxide on cardiovascular system. However, implementing and monitoring these possible effects during the study increases the safety profile of the study

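### Section 6.1 fixes one flat atropine dose, 0.2 mg iv, for bradycardia at every age from 1 to 16 years, with no size scaling and no word on repeat dosing

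*Protocol*

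**What the plan says.** Section 6.1 of the protocol has three lines on managing side effects:

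- "desaturation – supplemental oxygen via face mask"
- "hypotension – iv fluids, vasoactive drugs if needed"
- "bradycardia – atropine 0,2 mg iv"

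Only the third states an amount. Section 4.2 admits children from 1 to 16 years, and section 4.3 confirms the limits by excluding "Age <1 year or > 16 years". No section scales the 0.2 mg to weight or age, sets a maximum, or says whether it is a first dose or may be repeated.

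Two neighbouring rules do depend on age. The opening of section 6 sets the gas flow from an age-appropriate minute volume. The end of section 5.1.2 states that "Hypotension, hypertension, bradycardia, tachycardia are defined in accordance to age", without giving thresholds.

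The note closing section 6.1 says that "side effects such as hypotension, bradycardia are not expected to occur", but keeps monitoring for them as a safety measure.

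**The concern.** A flat amount in milligrams is a rule, not a missing detail. Read literally, a one-year-old and a sixteen-year-old with bradycardia receive the same 0.2 mg. Whatever dose per kilogram is right, one amount cannot deliver it across that range of body size. The oxygen and hypotension lines leave the amount to the treating clinician; the atropine line does not.

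The same part of the protocol recognises that children of different ages need different settings, because it adapts the gas flow. The rescue dose is the one stated quantity that was not adapted.

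At stake is the clarity of an emergency instruction for a side effect that the study monitors. Nothing statistical depends on it.

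**Working it through.** The protocol has no derivation of the 0.2 mg to reproduce. The check is a reading of the text followed by a division.

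**Inputs**

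- Dose: 0.2 mg iv (section 6.1).
- Age range: 1 to 16 years (sections 4.2 and 4.3).
- Body weights: not in the protocol. Assumed here as 10 kg at age 1 (range 8 to 12 kg) and 60 kg at age 16 (range 45 to 80 kg). The 20 kg and 40 kg rows are intermediate weights, not tied to an age.

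**Step 1. Dose per kilogram = 0.2 mg / weight**

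| Assumed weight | Calculation | mg/kg |
|---|---|---|
| 8 kg | 0.2 / 8 | 0.0250 |
| 10 kg | 0.2 / 10 | 0.0200 |
| 12 kg | 0.2 / 12 | 0.0167 |
| 20 kg | 0.2 / 20 | 0.0100 |
| 40 kg | 0.2 / 40 | 0.0050 |
| 45 kg | 0.2 / 45 | 0.0044 |
| 60 kg | 0.2 / 60 | 0.0033 |
| 80 kg | 0.2 / 80 | 0.0025 |

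**Step 2. Spread between smallest and largest child**

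Spread = (0.2 / w₁) / (0.2 / w₁₆) = w₁₆ / w₁, where w₁ and w₁₆ are the weights at ages 1 and 16. The 0.2 mg cancels, so the spread is the weight ratio and would be the same for any flat dose.

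- Central weights: 60 / 10 = 6.0
- Narrowest pairing: 45 / 12 = 3.75
- Widest pairing: 80 / 8 = 10

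**Step 3. What equal dosing per kilogram would need (illustration only)**

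If the 0.02 mg/kg that a 10 kg child receives were held constant, the amounts would be 0.02 × 20 = 0.4 mg, 0.02 × 40 = 0.8 mg and 0.02 × 60 = 1.2 mg. This shows how far a flat amount departs from a scaled one. It does not recommend 0.02 mg/kg; the protocol gives no reference dose.

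**Step 4. The rules side by side**

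| Item | Where | Depends on age or size? |
|---|---|---|
| Gas flow | Section 6 | Yes, by age |
| Heart rate that counts as bradycardia | Section 5.1.2 | Yes, by age |
| Oxygen, iv fluids, vasoactive drugs | Section 6.1 | No amount stated |
| Atropine | Section 6.1 | No: 0.2 mg for all |

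**The case against.** The strongest reply is that no error in the dose has been shown. The protocol contains no atropine reference dose, so nobody can conclude from it that 0.2 mg is wrong for a given child. The spread in mg/kg merely restates that children differ in size, and every weight behind it is assumed. This stands in part. A reader might infer that the dose is too small for adolescents or too large for toddlers; the protocol supports neither. What remains needs no reference dose: one amount cannot give comparable dosing per kilogram across ages 1 to 16.

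A second tempting inference is that the flat dose contradicts the age-based definition of bradycardia. It does not. That definition sets when a heart rate counts as bradycardia; it says nothing about how much drug to give. An age-specific trigger and a fixed dose can coexist. Nor do the age bands of the pain scales ("FLACC up to 4 years, FACES 4-9 years and Numeric Pain Rating Scale 9-16 years") have any bearing on atropine.

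Third, 0.2 mg may be meant as a first dose to be repeated as needed, by anaesthesia and intensive care staff who would adjust it anyway. Nothing in section 6.1 forbids that. If so, the spread above describes the first dose and not the total treatment. But the line does not say so, and staff who adjust are departing from the only figure written down.

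Finally, bradycardia is not expected, so the line would seldom be used. That limits the importance of the point. It does not mend an instruction meant for the occasion when bradycardia does occur.

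**Conclusion.** The point holds in a narrow form. Section 6.1 prescribes one absolute atropine dose for all eligible children, does not scale it to size and does not say whether it is an initial or a repeatable dose. Taken literally, the dose per kilogram falls about sixfold between a 10 kg and a 60 kg child, and 3.75-fold to 10-fold over the other weights considered. The direction rests only on older children being heavier; the size rests on the assumed weights.

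The finding is neither an internal contradiction nor evidence that 0.2 mg is the wrong dose for any particular child. It is a minor, cheap patient-safety improvement. It has no effect on the primary or secondary endpoints, the 300 planned occasions (section 4.4) or the analysis (section 7).

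**What to change.** In section 6.1, replace the flat figure with a weight-based dose, for example: *bradycardia: atropine [x] mg/kg iv, minimum [a] mg, maximum [b] mg; may / may not be repeated [conditions]; dose worked out from the child's weight before the gas is started.* The responsible clinicians should supply the values; none is proposed here because the protocol gives no basis for one.

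The cost is a one-line amendment, plus one weight and one calculation per child before the gas is started. The summary mentions "prospective collection of demographic data", which may already include weight, but the protocol does not list the items, so this should be confirmed. Recruitment, outcome definitions and data analysis stay as they are.

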7. STATISTICS

Descriptive statistics will be used to describe baseline characteristics. Categorical variables will be expressed as n (%), continuous variables as median [IQR]. Depending on data distribution parametric or nonparametric test will be used to explain relationship regarding outcome variables.

8. SAFETY REPORTING

8.1. Definition in matter of Pharmacovigilance

8.1.1. Adverse event

An adverse event is an undesirable experience occurring during the administration of a medicine for which the causal relationship with the administration of the medicine does not have to be proven. An adverse event is any unintended and undesirable signal (e.g. abnormal laboratory findings), symptom or disease that is time-related to the administration of a medicine.

A serious adverse event is any undesirable reaction/event with the following results:

Death

Immediate life-threatening situation,

Permanent or significant disability/incapacity,

Requires hospitalization or prolongation of existing hospitalization,

Is a congenital anomaly or birth defect,

Other medically significant condition.

8.1.2. Interaction

Interaction is a change in the pharmacokinetic or pharmacodynamic properties of a medicine caused by the concurrent administration of another medicine, food, or any other substance.

8.1.3. Special situations:

- Overdose is the administration of a medicine in a single or daily dose in an amount that exceeds the maximum recommended individual or daily dose according to the Summary of Product Characteristics and Patient Information Leaflet, including cumulative effects due to overdose.
- Unauthorized administration (Off label use) of a medicine is the administration of a medicine with marketing authorization, that is administered in a therapeutic indication, dosage or manner not listed in the Summary of Product Characteristics, or not approved.
- Abuse of a medicine is the permanent or occasional, intentional excessive use of a medicine followed by harmful physical or psychological effects.
- Medical error is any unintentional error in prescribing, issuing or administration of a medicine by a healthcare professional or patient.

- Occupational exposure to a medicine is the work-related exposure of a person to a medicine.
- Misuse of a medicinal product are situations where a medicinal product is intentionally and inappropriately used not in accordance with the terms of the marketing authorisation
- Lack of efficacy is an effect which is less than the expected action of the Product

